11.2. Loss to Follow Up

A participant will be considered lost to follow-up if they fail to return for scheduled visits and are unable to be contacted by the study site.

The following actions must be taken if a participant fails to return to the clinic for a required study visit:

[figure not shown]
- The site must attempt to contact the participant and reschedule the missed visit as soon as
 possible and counsel the participant on the importance of maintaining the assigned visit
 schedule and ascertain whether or not the participant wishes to and/or should continue in
 the study.
- Before a participant is deemed lost to follow up, the investigator or designee must make
 every effort to regain contact with the participant (where possible, 3 telephone calls and, if
 necessary, a certified letter to the participant's last known mailing address or local
 equivalent methods). These contact attempts should be documented in the participant's
 medical record.
- Should the participant continue to be unreachable, they will be considered to have withdrawn from the study with a primary reason of lost to follow-up.

For the purposes of the 6-month and 1-year follow-up, any participant who may have died within 6-months or 1 year of their index BCS procedure or for whom follow-up data cannot be retrieved (either through medical record review and/or telephone contact with the participant), will be considered lost to follow-up for the extension phase of the study. Data from participants that are lost to follow-up for the extension phase will still be used for analysis of all endpoints that are based upon data collected through the Month 3 visit.

12. Study Procedures and Schedule

- Immediate safety concerns should be discussed with spmd immediately upon occurrence or awareness to determine if the participant should continue or discontinue study treatment.
- Adherence to the study design requirements, including those specified in the Schedule of Activities, is essential and required for study conduct.
- All screening evaluations must be completed and reviewed to confirm that potential participants meet all eligibility criteria. The investigator will maintain a screening log to record details of all participants screened and to confirm eligibility or record reasons for screening failure, as applicable.

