- p. Any unresolved AEs present at Week 2 visit will be followed for an additional 7 days. Any unresolved SAEs will be followed for an additional 30 days. Patients with elevated liver enzymes will be followed until levels return to baseline.
- q. Medical chart reviewed to identify additional therapies related to the breast cancer diagnosis received since the Week 2 visit and within 1 year following Day 1 (e.g. additional surgeries, chemotherapy, radiation therapy, endocrine therapy, immunotherapy). In the event the patient is no longer under the care of the study investigator, the patient will be contacted via telephone.
- r. 3-month follow-up data must be collected 80-90 days post-procedure or within 7 days prior to commencement of radiation therapy, whichever occurs first.
- s. Includes assessment of neurological AEs (neurological AEs observed in the clinical trials of ALA HCl used for the visualization of glioma during surgical resection may be attributable to the greater amount of tissue resected in patients in the ALA arm as compared to control and are not expected to occur in breast cancer patients; nevertheless investigators must evaluate potential neurological AEs at each AE assessment time point)

SBI-CIP 20-002	Rev: v1.8	A prospective multi-center clinical study evaluating the use of PD G 506 A and the Eagle V1.2 Imaging System for the visualization of carcinoma during breast conserving surgery	Page: 65 of 157
-----------------------	--------------	--	-----------------

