12.7. Week 2 Visit (Day 10 – 14)

Clinical usefulness and diagnostic performance endpoint data will be collected at the participant's post-operative surgical follow-up visit.

At this visit, the participant will complete the post-operative Breast Conserving Therapy Module of the Breast-Q survey. To minimize the potential impact of timing of administration of the Breast-Q survey post-op questionnaire, all patients will complete the 2-week post-op questionnaire before they have met with their *surgeon* to discuss their surgical pathology report.

The participant's surgical pathology report will be available at this time. Endpoint data will be retrieved from the participant's surgical pathology report and the study-specific Pathology Data Collection Tool. Additional data related to the final pathological tumor staging, pathological features/characteristics and nodal involvement will be retrieved from the participant's surgical pathology report and recorded in the eCRF.

The *surgeon* will question the patient about any patient-reported Aes and use of concomitant medications as well as assess and record any ongoing adverse events in the participant's medical record and eCRF.

Blood work (CBC, AST, ALT, TBL, creatinine) will be performed at this visit. If liver enzymes are elevated from baseline (and deemed clinically significant according to the **Table 12.2** below), the patient will be followed until such time that liver enzyme levels return to baseline. Physical examination must include assessment of any phototoxicity reactions and any observed phototoxicity reactions will be followed until resolution.

Table 12.2: Criteria for clinical significant liver enzyme elevation

	SBI-CIP 20-002	Rev: v1.8	A prospective multi-center clinical study evaluating the use of PD G 506 A and the Eagle V1.2 Imaging System for the visualization of carcinoma during breast conserving surgery	Page: 77 of 157
--	-----------------------	--------------	--	-----------------

Criteria	CTCAE v5.0 Grade 2 (moderate) as criterium to judge if elevation of liver enzymes should be deemed clinically significant
Bilirubin: above upper limit of normal	Bilirubin:
	> 1.5 – 3.0x institutional* ULN if baseline normal
	> 1.5 – 3.0x baseline if baseline abnormal
AST: > 2.5x institutional ULN	AST:
	> 3.0 – 5.0x institutional* ULN if baseline normal
	> 3.0 – 5.0x baseline if baseline abnormal
ALT: > 2.5x institutional ULN	ALT:
	> 3.0 – 5.0x institutional* ULN if baseline normal

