13.3. Time Periods and Frequency for Event Assessment and Follow-Up

The occurrence of an (S)AE may come to the attention of study personnel during study visits and interviews of a study participant presenting for medical care, or upon review by a study monitor. All AEs including local and systemic reactions not meeting the criteria for SAEs will be captured as described in Sections 13.2 and 13.4.2.

Although the neurological AEs observed in the clinical trials of ALA HCl used for the visualization of glioma during resection surgery may be attributable to the greater amount of tissue resected in patients in the ALA arm as compared to control, Investigators are asked to assess for potential neurological AEs, in addition to other AEs, at each AE assessment time point.

The PI will record all reportable events with start dates occurring any time after the participant has signed the informed consent form until the Week 2 Visit. If an (S)AE is recorded at the Week 2

SBI-CIP 20-002 Rev: v1.8 A prospective multi-center clinical study evaluating the use of PD G 506 A and the Eagle V1.2 Imaging System for the visualization of carcinoma during breast conserving surgery	Page: 86 of 157
---	-----------------

Visit the participant will continue to be assessed for an additional 7 (for non-serious AEs) or at least 30 calendar days (for SAEs) after the Week 2 visit. If liver enzymes are elevated at the Week 2 visit (as defined in Section 12.7), the patient will be followed until such time that levels return to baseline. At each visit, the *surgeon* investigator will inquire about the occurrence of AE/SAEs since the last visit. Events will be followed for outcome information (Section 13.2.4). SAEs will be followed until resolution or stabilization. Clinical laboratory tests (e.g. blood panels) and other relevant medical tests (e.g. ECG) may be ordered to investigate a (S)AE if clinically warranted. Events occurring after the Week 2 Visit will not be recorded or reported as part of the study protocol.

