13.4.1. Documentation Procedures and Reporting Obligations to the Sponsor

13.4.1.1. Adverse Events

The Investigator must document all AEs that occur during the observation period set in this protocol (Section 13.3) on the pages provided in the eCRF. Additional specific instructions may be provided in the investigator file and in the case report form itself.

All AEs (whether serious or not) must be documented on the "Adverse Event" page of the Case Report Form (CRF). All AEs will be described using the sign, symptom, or medical diagnosis on the AE ICRF in standard medical terminology in order to avoid the use of vague, ambiguous, or colloquial expressions. Each AE will be defined as serious or non-serious according to the definitions in Section 13.1.2. The investigator will evaluate the severity of each AE and causal relationship of the event to the Investigational Device (Eagle V1.2 Imaging System)/ Investigational Drug (PD G 506 A)/Surgical Procedure/ Other study-specific procedures (assessed only by those with the training and authority to make a diagnosis), and time of resolution/stabilization of the event. All AEs occurring while on study beginning after the study patient has signed the informed consent form must be documented appropriately regardless of relationship. All AEs will be followed to adequate resolution, as defined by the participant's treating *surgeon*.

Changes in the severity of an AE will be documented to allow an assessment of the duration of the event at each level of severity to be performed. AEs characterized as intermittent require documentation of onset and duration of each episode.

Adverse Events exempted from reporting:

Any medical condition that is present at the time that the participant is screened will be considered as baseline and not reported as an AE. However, if the study participant's baseline condition deteriorates during the study any time after administration of the investigational drug, it will be recorded as an AE. SAEs and Ups will be recorded in the safety data collection system throughout the study.

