and submitted to the sponsor within 24 hours of learning of a participant's pregnancy. The investigator will request written permission to follow the participant until the outcome of the pregnancy. The investigator will collect follow-up information on the participant and the neonate and the information will be forwarded to the sponsor. Generally, follow-up will not be required for longer than 6 to 8 weeks beyond the estimated delivery date. Any termination of pregnancy will be reported, regardless of fetal status (presence or absence of anomalies) or indication for the procedure.

While pregnancy itself is not considered to be an AE or SAE, any pregnancy complication or elective termination of a pregnancy will be reported as an AE or SAE. A spontaneous abortion is always considered to be an SAE and will be reported as such. Any post-study pregnancy related SAE considered reasonably related to the study treatment by the investigator will be reported to the sponsor as described in Section 13. While the investigator is not obligated to actively seek this information in former study participants, they may learn of an SAE through spontaneous reporting.

Any participant that becomes pregnant following consenting to participate and prior to receiving the investigational drug, will be terminated immediately. If a participant becomes aware that they are pregnant following administration of the investigational drug but prior to completing the study, they will complete the study according to the protocol.

SBI-CIP 20-002	Rev: v1.8	A prospective multi-center clinical study evaluating the use of PD G 506 A and the Eagle V1.2 Imaging System for the visualization of carcinoma during breast conserving surgery	Page: 140 of 157
-----------------------	--------------	--	------------------

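### Section 13.3 bars recording or reporting any event after Week 2, against other sections on SAE reporting, and Section 11.2 files deaths as extension-phase loss to follow-up

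*Combined protocol and SAP*

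**What the plan says.** **Recording window.** Section 13.3 has the investigator record events whose start date lies between signed consent and the Week 2 visit, which Section 12.7 places at Day 10 to 14. It ends: "Events occurring after the Week 2 Visit will not be recorded or reported as part of the study protocol".

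**Other rules on the same events.**
- Section 13.4.1.1: "SAEs and Ups will be recorded in the safety data collection system throughout the study". It also asks for documentation of AEs that occur while the patient is on study.
- Section 13.4.1.2 requires every SAE, related or not, to go to the safety vendor within 24 hours of awareness. It sets no end date.
- Appendix 5: "Any post-study pregnancy related SAE considered reasonably related to the study treatment by the investigator will be reported to the sponsor".

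**Length of the study.** Section 8.2 counts a patient as complete only once one-year data are in hand. It ends the study for efficacy at the last patient's 3-month data and calls the rest an extension phase.

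**Deaths.** For the 6-month and 1-year follow-up, Section 11.2 takes "any participant who may have died within 6-months or 1 year of their index BCS procedure" together with anyone whose follow-up data cannot be retrieved, and treats both as lost to follow-up in the extension phase. Their data still serve endpoints that use information through Month 3.

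**Later contacts.** The chart reviews in Sections 12.8 and 12.9 name treatments for the primary breast cancer. They name neither adverse events nor vital status.

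**Unresolved events.** Footnote p of the Schedule of Activities: "Any unresolved AEs present at Week 2 visit will be followed for an additional 7 days". Section 13.4.1.1: "All AEs will be followed to adequate resolution", as judged by the treating surgeon.

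**The concern.** Section 13.3 sets a limit on what the site looks for, but its last sentence also limits what the site may write down once it knows. An investigator who learns of a related SAE that began after the Week 2 visit meets one section that says not to record or report it and two that say to do both.

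Three things depend on which rule is followed:

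- **Safety endpoints.** P(S.1) to P(S.3) count procedure-, drug- and device-related events of grade 3 to 5. An event kept out of the database is kept out of these counts. Comparing safety between arms is one of the stated purposes of Arm 1 (Section 8.1), and Arm 2 patients may lose more tissue (Section 6.2.6).
- **The suspension trigger.** Section 13.5 suspends dosing when a drug- or device-related SAE is reported to the safety vendor. It works only if the report is made.
- **Deaths.** No current text has a new death after Week 2 recorded as a death. The only rule that mentions one calls it loss to follow-up.

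**Working it through.** The plan states no figure on this point, so there is none to reproduce. The check is to run concrete cases through the text.

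| Case (Week 2 visit on Day 14) | Section 13.3 | Other sections | Result |
|---|---|---|---|
| SAE starts Day 8, patient dies of it Day 40 | In the window; followed until it resolves or stabilises | 13.2.4 has a fatal outcome category | Captured |
| Related SAE starts Day 15, site learns Day 20 | Not recorded or reported | 13.4.1.1: record. 13.4.1.2: report within 24 hours of awareness. 13.4.2.2 and 13.4.2.3: onward reporting of qualifying events, no Week 2 limit | Contradictory |
| Death from an event starting after Week 2, found at the 6- or 12-month chart review | Not recorded or reported | 12.9: review names treatments only. 11.2: lost to follow-up in the extension phase | Not recorded as a death, unless 13.4.1.1 and 13.4.1.2 are held to override 13.3 |
| Related pregnancy SAE after the study | Not recorded or reported | Appendix 5: report | Contradictory unless read as an exception, which 13.3 does not state |

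**Endpoint P(2.15).** Its denominator is all patients in the arm. Suppose a patient dies at month 8 without a second operation. The formula, taken literally, counts her as not re-operated. Section 11.2 calls her lost to follow-up. Section 15.4.1 says missing data will be imputed and defers the details. These could give different numerators or denominators, and the text does not choose. Nor does it say whether a re-operation known before death still counts.

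**Unresolved events.** For SAEs, footnote p and Appendix 2 give 30 additional days. Section 13.3 says at least 30, then until resolved or stable. These can be read together. For non-serious AEs, footnote p, 13.3 and Appendix 2 give 7 additional days, while 13.4.1.1 follows all AEs until adequately resolved. That conflict remains.

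**Share of follow-up inside the window.** Week 2 day divided by last day of follow-up:
- Shortest: 10 / 379 = 2.6%. Longest: 14 / 365 = 3.8%.
- Against the 3-month visit (Day 80 to 90) only: 10 / 90 = 11.1% to 14 / 80 = 17.5%.

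**Illustrative deaths (assumption only).** Let r be an assumed one-year risk of death, spread evenly over the year. The risk after Day 14 is q = r × (365 − 14) / 365. In 500 Part B patients the expected count is 500q, and the chance of at least one is 1 − (1 − q)^500.
- r = 0.2%: q = 0.00192, about 1.0 death, chance of at least one 0.62.
- r = 1%: q = 0.00962, about 4.8 deaths, chance 0.99.
- r = 2%: q = 0.01923, about 9.6 deaths, chance above 0.99.

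The finding does not depend on these values.

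**The case against.** The strongest reply is that the Week 2 limit is a deliberate and mostly consistent safety window. The AE row of the Schedule of Activities ends at Week 2, the last in-person visit. Inclusion criterion 5 and Sections 12.4.1 and 12.4.5 define the study period as ending there, and Section 12.10 follows early terminations to the same point. Section 13.4.1.1 opens by tying AE documentation to the period in 13.3, and its sentence on SAEs for the whole study could be read inside that period. Exposure is one oral dose and one operation, with light precautions of 48 hours. The pregnancy rule is a natural special case.

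This stands for routine AEs, and nothing here asks for a longer routine window. It does not rescue the last sentence of 13.3, which covers all events, serious and related ones included. Reading the word study in 13.4.1.1 as ending at Week 2 also needs a definition that the protocol does not give, since Section 8.2 uses the same word for a period to 3 months and to one year.

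A reader might infer three stronger things that the documents do not support:
- *That a late SAE is unable to reach the vendor or DSMB.* Sections 13.4.1.2, 13.4.2.2 and 13.4.2.3 carry no Week 2 limit, so reporting is contradictory, not impossible.
- *That every late death is lost.* A death from an SAE that began by Week 2 is captured, and the rule in 11.2 is worded for the extension phase. It does not prescribe how the case report form codes disposition.
- *That late deaths would be absorbed in the 5% loss allowance.* That allowance inflates a sample size driven only by P(1.1), which rests on operative pathology. It does not forecast extension-phase losses.

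**Conclusion.** The point holds in a limited form. The current text gives contradictory instructions for SAEs that start after Week 2 and become known to the site. If 13.3 is followed, related SAEs and deaths of this kind stay out of P(S.1) to P(S.3) and, where drug- or device-related, do not trigger the suspension in 13.5. Section 11.2 merges death with unretrievable data for the extension phase and leaves P(2.15) undefined for patients who die within the year. Among the rules for following unresolved events, only the one for non-serious AEs is in real conflict.

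The size cannot be put as a number of missed events. The 2.6% to 3.8% is a share of days, and risk from a single dose and operation is probably concentrated early. The documents give no death rate, so any death count is an assumption. The primary endpoint is not affected.

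**What to change.** - **Section 13.3:** limit the last sentence to routine AEs. Add that deaths, and SAEs the investigator judges related to drug, device or study procedure, are recorded and reported by the existing SAE route when the site learns of them after Week 2, including at the 3-, 6- and 12-month chart reviews. State when this period ends.
- **Sections 13.4.1.1, 13.4.1.2 and Appendix 5:** refer to that one rule, name the pregnancy provision as an exception, and use one defined term for the study period.
- **Section 11.2:** remove death from the loss-to-follow-up definition and record it as its own disposition, with date and cause.
- **P(2.15):** state how a patient who dies within the year counts, with and without an earlier second operation.
- **Unresolved non-serious AEs:** reconcile footnote p, 13.3 and Appendix 2 with 13.4.1.1. The choice of rule is for the sponsor.

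The cost is protocol wording, a vital-status field, and one question on related SAEs at chart reviews that are already scheduled. The downside is a few extra SAE forms and possibly extra DSMB reviews, since a late drug- or device-related SAE would then clearly trigger the suspension in 13.5.

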13.4. Reporting Procedures

This section and subsequent sub-sections describe:

- 1. Documentation Procedures and Reporting Obligations to the Sponsor;
- 2. Regulatory Reporting Obligations to the Competent Authorities (Health Canada & FDA) and the Ethics Committees (REBs & IRBs)

13.4.1. Documentation Procedures and Reporting Obligations to the Sponsor

13.4.1.1. Adverse Events

The Investigator must document all AEs that occur during the observation period set in this protocol (Section 13.3) on the pages provided in the eCRF. Additional specific instructions may be provided in the investigator file and in the case report form itself.

All AEs (whether serious or not) must be documented on the "Adverse Event" page of the Case Report Form (CRF). All AEs will be described using the sign, symptom, or medical diagnosis on the AE ICRF in standard medical terminology in order to avoid the use of vague, ambiguous, or colloquial expressions. Each AE will be defined as serious or non-serious according to the definitions in Section 13.1.2. The investigator will evaluate the severity of each AE and causal relationship of the event to the Investigational Device (Eagle V1.2 Imaging System)/ Investigational Drug (PD G 506 A)/Surgical Procedure/ Other study-specific procedures (assessed only by those with the training and authority to make a diagnosis), and time of resolution/stabilization of the event. All AEs occurring while on study beginning after the study patient has signed the informed consent form must be documented appropriately regardless of relationship. All AEs will be followed to adequate resolution, as defined by the participant's treating *surgeon*.

Changes in the severity of an AE will be documented to allow an assessment of the duration of the event at each level of severity to be performed. AEs characterized as intermittent require documentation of onset and duration of each episode.

Adverse Events exempted from reporting:

Any medical condition that is present at the time that the participant is screened will be considered as baseline and not reported as an AE. However, if the study participant's baseline condition deteriorates during the study any time after administration of the investigational drug, it will be recorded as an AE. SAEs and Ups will be recorded in the safety data collection system throughout the study.

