10.1.2.5. Preparation and Administration of the Placebo

Participant's randomized to Arm 1 will receive drinking water as the placebo. Calculate the administration volume, in mL, according to the following:

Administration Volume (mL) =
$$\frac{Patient\ Weight\ (kg) \times 20\ ml}{30\ kg}$$

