10.1.2.6. Route of Administration

The investigational drug and placebo will be provided by an oral route of administration.

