12.4. Surgical Procedure (Day 1)

12.4.1. Pre-operative Procedures

Participants will arrive at the site at least 4 hours prior to surgery. Participant eligibility and documented informed consent will be verified. If the day of surgery weight is being used for calculating the investigational drug administration volume, it will be collected and communicated to an unblinded qualified medical professional (e.g. pharmacist) responsible for preparing and dispensing the investigational drug or placebo (Sections 10.1.2.3, 10.1.2.4, 10.1.2.5). If the weight used for calculating the investigational drug administration volume was collected prior to day 1 but within 7 days of surgery (Section 12.2), the participant's day of surgery weight must still be collected and recorded on the eCRF. In women of child-bearing potential (WOCBP) a negative pregnancy test result must be documented prior to administration of the investigational drug or placebo. The investigational drug or placebo will be administered by a blinded qualified medical professional (e.g. nurse). Participants will be administered PD G 506 A or placebo approximately 3 hours (2-4 hr) prior to anesthesia. Neither the *surgeon* nor *surgeon's assistant* can administer the study drug due to the potential risk that the patient's reaction to consuming the investigational product accidentally unblinds the individual dosing them. Patients must have an IV line in place prior to study drug administration, and must be under medical supervision from the time of dosing until the initiation of anesthesia. Baseline heart rate and blood pressure will be collected prior to administration and post-administration heart rate and blood pressure will be monitored and recorded immediately after and 30 minutes after administration. Post-administration heart rate and blood pressure will continue to be collected at least hourly following the measurement at 30-mins post dosing, until the initiation of anesthesia. The participant will be observed for 30 minutes following administration for any acute (S)AE(s). (S)AE monitoring will continue for the duration of the study period (until the Week 2 visit) as described in Section 13

Instructions will be provided to the patient to immediately report any possible symptoms of hypotension (e.g. light headedness, blurry vision, nausea, dizziness, weakness, blurry vision, etc.) after receiving the study drug.

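### The rule for recording a worsened baseline condition starts at dosing with the investigational drug, which conflicts with the protocol's consent-based AE window and, read literally, leaves non-serious worsening in Arm 1 without a trigger

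*Combined protocol and SAP*

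**What the plan says.** Under the exemptions in protocol Section 13.4.1.1, "Any medical condition that is present at the time that the participant is screened will be considered as baseline and not reported as an AE". The next sentence brings worsening back in: if the "baseline condition deteriorates during the study any time after administration of the investigational drug, it will be recorded as an AE". The sentence after that has SAEs and unanticipated problems recorded throughout the study, with no link to dosing.

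Two other rules set a different start:

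- Section 13.3 has the investigator record reportable events that start "any time after the participant has signed the informed consent form until the Week 2 Visit".
- Section 13.4.1.1, ahead of the exemption, says: "All AEs occurring while on study beginning after the study patient has signed the informed consent form must be documented appropriately regardless of relationship".

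On the products, Section 10.1.2.5 says that those "randomized to Arm 1 will receive drinking water as the placebo". Some sections name both products: "The investigational drug and placebo will be provided by an oral route of administration" (10.1.2.6), and a "negative pregnancy test result must be documented prior to administration of the investigational drug or placebo" (12.4.1).

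**The concern.** An AE collection rule should start at the same moment, and mean the same thing, in every arm being compared. This one has two faults.

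First, its start point (dosing) differs from the start point used everywhere else for AEs (consent). A site cannot tell whether a condition that worsens between consent and dosing is to be entered.

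Second, the start is tied to a product that Arm 1 does not receive. A site that follows the words literally would enter non-serious worsening for Arm 2 and have no prompt to do so for Arm 1. Comparing safety between arms is one of the stated purposes of the SoC arm (Section 8.1), and Section 15.8 summarises safety by treatment arm. If capture differed by arm, the drug arm would look worse than it is on that class of event. Blinding would not prevent this. The surgeon is unblinded when the SoC lumpectomy is complete (Section 10.3), and it is the surgeon who assesses AEs at the Week 2 visit (Sections 12.4.5 and 12.7).

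**Working it through.** The plan gives no figure on this point, so the check is mainly a comparison of texts.

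**1. Start of recording**

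| Text | Start | Tied to the drug? |
|---|---|---|
| 13.3, recording window | Consent, to Week 2 | No |
| 13.4.1.1, general AE rule | Consent | No |
| 13.4.1.1, SAEs and unanticipated problems | Throughout the study | No |
| 13.1.1, note on planned surgical measures | Known condition exempt only if it has not worsened during the study | No |
| 13.4.1.1, worsening of a baseline condition | Administration of the investigational drug | Yes |

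The last row is the only one that starts at dosing. Screening can begin up to 90 days before surgery (Section 12.2), so the interval between consent and dosing can be long. This conflict is the same in both arms and does not depend on how the drug term is read.

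**2. Does the trigger apply in Arm 1?** The AE paragraph of 13.4.1.1 itself identifies the investigational drug as PD G 506 A. Arm 1 receives water. On the literal reading the trigger is never met in Arm 1; on the shorthand reading, in which the term covers either product, it is met in both arms.

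**3. Which events could be affected?** Serious worsening drops out, because SAEs are recorded throughout. What remains is non-serious worsening of a condition already present at screening.

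**4. Which outputs could be affected?** The safety endpoints in Section 7.4 are procedure-, drug- and device-related events of grade 3 to 5, and 15.8 summarises them descriptively by arm. Non-serious worsening reaches those only if it is also grade 3 or higher and judged related. Section 7.4 also lists AEs in general as a safety assessment, and 15.8 allows further summaries. An all-AE table by arm is where a difference in capture would mainly show.

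**5. Illustration, on assumed rates.** Inputs: arm sizes of 72 and 428 (Section 15.2); an assumed true rate r of non-serious worsening, equal in both arms; the literal reading applied at every site. Expected events are 72 × r in Arm 1, none of them recorded, and 428 × r in Arm 2, all recorded.

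| Assumed r | Arm 1 true, 72 × r | Arm 1 recorded | Arm 2 recorded, 428 × r |
|---|---|---|---|
| 1% | 0.7 | 0 | 4.3 |
| 2% | 1.4 | 0 | 8.6 |
| 5% | 3.6 | 0 | 21.4 |
| 10% | 7.2 | 0 | 42.8 |

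The artificial difference equals r itself: 1 to 10 percentage points over this range. These are worst cases under the literal reading and assumed rates, not estimates for the trial.

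**The case against.** A reader might infer that worsening in Arm 1 goes unrecorded altogether, and that the drug arm will therefore show a spurious excess of AEs of a definite size. The case against that reading is strong.

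- **Usage.** The protocol often writes of the investigational drug when it must mean either product. A blinded surgeon completes the investigational drug prescription for every enrolled participant (12.3). Light exposure is limited after administration of the investigational drug (12.4.1), which would break the blind if done in Arm 2 only. The sunscreen advice (10.5, 12.4.5) and the early termination rules (12.10) are worded the same way. A drafting shorthand is plausible.
- **Logic.** The sentence says that worsening after dosing is recorded. It does not say that other worsening is not.
- **Other rules.** The consent-based rules in 13.3 and 13.4.1.1 cover both arms, and serious worsening is captured in both.
- **Unseen instructions.** Section 13.4.1.1 refers to further instructions in the investigator file and case report form, which may settle the matter.

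All of this stands against the strong reading. It does not make the sentence sound. The sentence sits under an exemption from reporting, so a site can reasonably let it override the general rule. The same section identifies the drug as PD G 506 A. Some safety text really does depend on having received it: Section 11.1 continues safety collection after withdrawal for participants who have received PD G 506 A. And the shorthand reading leaves the conflict between consent and dosing where it was.

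**Conclusion.** The point holds as a conflict within the document. The dosing-based start for worsening of a baseline condition disagrees with the consent-based start in 13.3 and in 13.4.1.1, whichever way the drug term is read. Unequal capture between arms is a possible consequence. It requires that sites take the sentence literally and let it override the general rules.

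The documents do not support the conclusion that all worsening in Arm 1 is lost, because serious events are recorded in both arms and the general rules cover Arm 1. Nor do they support any particular excess in AE rates: they give neither an AE rate nor the share of AEs that are worsening of existing conditions. The size is therefore unknown. It is limited to non-serious worsening, falls mainly on all-AE summaries by arm, and can reach the named safety endpoints only through related events of grade 3 or higher that are not serious. The efficacy endpoints are unaffected. This is a minor point, worth correcting because the correction is nearly free.

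**What to change.** Reconcile the passages by rewording the sentence in 13.4.1.1 along these lines: *If a condition present at screening worsens at any time from signing of the informed consent form to the Week 2 Visit, the worsening is recorded as an AE, in the same way in both arms.* Where any reference to dosing is kept, it should name the investigational drug or placebo. A flag for events that start after dosing with either product would help the analysis but is optional.

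The cost is one sentence in the protocol, a matching line in the eCRF completion guide, and a few more AE entries.
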